### **9.1.4 Relatedness to Investigational Medicinal Product**

The relatedness of the event to enapotamab vedotin must be assessed by a physician. If relatedness changes over time, the last judgment by the investigator should be reported. Relatedness has to be assessed and reported from the first time the AE is being reported.

### **9.1.5 Start Date and Time**

Start date for (S)AEs is the date of occurrence of the first symptom of the disease, e.g., if chest pain occurs on 01 April 2016 and the patient is hospitalized with myocardial infarction on 04 April 2016, the onset date of the SAE myocardial infarction is 01 April 2016.

Document Name: GCT1021-01 Protocol

Document Number: TMF-03326

Version: 11.0

---

For laboratory AE's, the start date is the date the sample was taken.

Time should be filled in if event starts on a dosing day or if the duration of the event is less than 24 hours.

### **9.1.6 Outcome**

Outcome of the AE must be judged by investigator by the following terms:

- Fatal
- Not recovered/not resolved
- Recovered/resolved
- Recovered/resolved with sequelae
- Recovering/resolving
- Unknown

### **9.1.7 Action Taken with Investigational Medicinal Product**

Action taken with enapotamab vedotin should be measured as:

- Dose increased
- Dose not changed
- Dose reduced
- Dose interrupted
- Drug withdrawn
- Not applicable
- Unknown

Not applicable should only be used if the AE occurs before first treatment or in the follow-up period.

### **9.1.8 End Date and Time**

End date should be filled in if the outcome of an event is fatal, recovered/resolved, recovered/resolved with sequelae, recovering/resolving.

For laboratory AE's, the end date is the date a sample is taken, which shows a decrease in the NCI-CTCAE grade and is no longer considered clinically significant.

In case the local and central laboratory assessments of a sample taken on the same day differ with respect to AE resolution/grade change, the AE end date is determined by the central laboratory

Document Name: GCT1021-01 Protocol

Document Number: TMF-03326

Version: 11.0

---

assessment.

In case a sample is taken for local assessment, without a central assessment, and it shows that the laboratory AE has resolved, the end date will be the date the sample was taken. In case a central laboratory assessment taken after this date shows that the laboratory AE is not resolved, and it is considered clinically significant, then a new laboratory AE should be recorded, with start date entered as the date the sample for the central assessment was taken.

Time should be filled in if event starts on a treatment/dosing day or if the duration of the event is less than 24 hours.

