### **9.1.3 Intensity**

The investigator will use the NCI-CTCAE version 4.03 to describe the severity of the AE (NCI-CTCAE v4.03, 2010).

A persistent AE is one that extends continuously between patient evaluation timepoints without resolution. Such events should only be recorded once on the AE eCRF. Changes in intensity of an ongoing AE should be assessed at each visit or more frequent if deemed necessary. In case of a change in NCI-CTCAE grading, the new grading and date of change should be reported on the relevant Adverse Event eCRF (please refer to the instructions that accompany the AE eCRF for more information).

A recurrent AE is one that resolves between patient evaluation timepoints and subsequently recurs. Each recurrence of an AE should be recorded as a separate event on the AE eCRF.

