#### **10.3.6.1 Adverse Events**

AEs will be coded using the latest version of MedDRA available prior to clinical database lock and will be graded using NCI Common Terminology Criteria for Adverse Events (CTCAE) version 4.03. All AE summaries will be summarized (frequency counts and percentages) by system organ class and/or preferred term, and maximum severity grades, except where otherwise noted. Additional summaries of AEs will be specified in the SAP. A patient with multiple Common Terminology Criteria (CTC) grades for an AE will be summarized under the maximum CTC grade recorded for the event.

All AEs will be listed, and any other information collected (e.g., start/end dates and duration of AE, severity or relatedness to trial medication) will be listed as appropriate.

A safety overview table will be provided for all AEs collected during the entire trial.

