## 17.6 Follow-Up on Adverse Events

All AEs should be followed until they are resolved or until the Safety Follow-Up visit, whichever comes first. Related AEs meeting one of the serious criteria, and still ongoing after ended trial

Document Name: GCT1021-01 Protocol

Document Number: TMF-03326

Version: 11.0

---

participation should be followed on a regular basis, according to the investigator's clinical judgment, until the event has been resolved or until the investigator assesses it as chronic and all queries have been resolved.

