In all tabulations, subjects will only be counted once for each preferred term. In case a subject experienced the same event more than once or has reported grade changes, the highest NCI-CTCAE grade will be presented.

In addition, time to onset of first AESI (for subjects with at least one event), total number of AESI events, total number and percentage of AESI events with outcome of resolution, and time to resolution of each AESI event (for events which are resolved) will be summarized by AESI type using descriptive statistics. AESI events with partial start date will be imputed accordingly to the rules described in section 4.7.

Time to onset of first AESI event will also be presented graphically by AESI type using a cumulative distribution function (one plot with one line for each AESI type); subjects with no AESI will not be included. This plot will also be presented for all subjects on 2.2 mg/kg across escalation and expansion and one for all subjects on 1.0 mg/kg across escalation and expansion.

For subjects with constipation, the number of subjects who did or didn't use prophylactic laxatives (based on diary data) will be tabulated.

For subjects with neutropenia, the number of subjects who did or didn't use G-CSF (based on concomitant medications) will be tabulated.

Treatment-emergent adverse events of special interest will also be presented in a table by type, cycle and preferred term and in a segmented bar-chart (each segment displays highest NCI-CTCAE grade with % of subjects who experience AESIs and related AESIs over time. Note: the % over time should be based on subjects still in the trial at the time of the corresponding cycle. When the same adverse event occurs more than once, only the first event will be included (similarity is defined based on the preferred term). Adverse events will be assigned to the cycle based on the onset date of this first AE. The highest NCI-CTCAE grade will take into account all occurrences of the same preferred term and all the individual grade changes as reported in the eCRF. The segmented bar-chart will also be produced for all subjects on 2.2 mg/kg across escalation and expansion and one for all subjects on 1.0 mg/kg across escalation and expansion.

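### The protocol asks for an end date on AEs that are only recovering; this truncates listed durations and, because the SAP does not define resolved, could inflate AESI resolution rates

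*Protocol*

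**What the plan says.** **Outcome codes.** Protocol section 9.1.6 gives six outcomes. "Recovering/resolving" is one of them, listed separately from recovered/resolved and from recovered/resolved with sequelae.

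**End date.** Section 9.1.8 states: "End date should be filled in if the outcome of an event is fatal, recovered/resolved, recovered/resolved with sequelae, recovering/resolving". Section 17.1.8, which applies from Amendment 10, repeats the sentence. For laboratory AEs only, section 9.1.8 adds that the end date is that of a sample "which shows a decrease in the NCI-CTCAE grade and is no longer considered clinically significant".

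**One record or several.** Section 9.1.3 says: "A persistent AE is one that extends continuously between patient evaluation timepoints without resolution". Such an event is recorded once, and grade changes are logged on that record. For an event that resolves and then comes back: "Each recurrence of an AE should be recorded as a separate event on the AE eCRF".

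**Follow-up.** Section 17.6 says: "All AEs should be followed until they are resolved or until the Safety Follow-Up visit, whichever comes first".

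**Use in the analysis.** Protocol section 10.3.6.1 lists for each AE "start/end dates and duration of AE, severity or relatedness to trial medication", and the AE listing in SAP section 17.2 carries duration, outcome and date of resolution. For AESIs, SAP section 17.2 also reports the number and percentage of events whose outcome is resolution, and "time to resolution of each AESI event (for events which are resolved"). SAP Addendum section 3.5 repeats this pair. Addendum section 3.6 analyses improvement separately, defined as a move to a lower grade.

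**The concern.** An end date says that an event is over, whereas the recovering/resolving code says that it is not. A record carrying both contradicts itself, and any quantity computed from the end date takes the wrong side.

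Two kinds of output are at stake. The first is AE duration, which is listed for every event. The second is the account of AESI reversibility, given by the percentage resolved and the time to resolution. The safety profile is part of the primary objective. Peripheral neuropathy is an AESI that section 9.1.9.3 says will be assessed to learn more about its clinical course. If events that were still present when last seen are shown as finished, toxicity looks shorter-lived than it was.

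**Working it through.** The plan gives no figure to reproduce, so the check follows the end-date rule through to each output that could use it.

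**1. Is the rule consistent with the rest of the protocol?** No. Under 9.1.6 a recovering event is distinct from a recovered one. Under 9.1.3 an event without resolution stays open as a single record. Under 9.1.8 and 17.1.8 the same event must be given an end date. For non-laboratory events such as neuropathy or constipation, the protocol does not say which date that should be, and no true end date exists yet. Because 17.6 lets AE follow-up stop at the safety follow-up visit, an event can still be recovering when last observed.

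**2. Listed duration.** The published SAP text gives no formula for AE duration. I assume end date − onset date + 1.

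- True duration = (date of actual resolution − onset + 1).
- Listed duration = (date entered while recovering − onset + 1).
- Shortfall = date of actual resolution − date entered. This is positive whenever the event was still present on the date entered.

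This holds however the AESI summaries are programmed.

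**3. Percentage of AESIs resolved.** Let p be the share of AESI events coded recovered/resolved (with or without sequelae) and r the share coded recovering/resolving with an end date. The documents do not give r, so it is an assumption.

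| Programming of resolved | Reported percentage | Overstatement |
|---|---|---|
| Recovered outcome codes only | p | 0 |
| End date present, or recovering counted as resolution | p + r | r |

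For r = 5%, 10% and 20% the second row gives 5, 10 and 20 points. As an illustration only, take 100 events of which 40 are recovered, 20 recovering and 40 not recovered. The result is 40/100 = 40% under the first reading and (40 + 20)/100 = 60% under the second.

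**4. Time to resolution.** Under the first reading recovering events drop out. Under the second, each contributes a time earlier than its true resolution. The direction of the resulting median is not fixed. Individual times are too short, but long-running events that would otherwise be excluded are added, and these can pull the median up.

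**5. Outputs not affected.** The incidence and highest-grade tables in SAP section 17.2 count subjects by occurrence and worst grade, not by resolution date. Improvement in Addendum section 3.6 rests on grade changes.

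**The case against.** The strongest reply is that the SAP already bases the percentage on an outcome of resolution and limits time to resolution to resolved events. Read plainly, recovering events are excluded and the inflation is zero. This stands as the more natural reading. It does not settle the matter, because neither the SAP nor its Addendum names the outcome codes or says that the end date plays no part.

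Other points on that side:

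- **Reach.** General AE duration is only listed, and the outcome appears in the same listing, so a careful reader can see that the event was recovering. This limits the harm, but the duration shown is still wrong.
- **Unseen instructions.** Section 9.1 refers to eCRF instructions that are not in the documents and may say which date to enter. They could soften the effect, but they cannot be assumed to override a sentence that the protocol states twice.
- **Timing.** According to Addendum section 2.1, data to 22 March 2021 have been reported, 3 subjects remained on treatment after that date, and the last safety follow-up ended on 12 November 2021. New site instructions would not change data already collected. An analysis rule still would.

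A reader might also infer that closing a recovering event turns later worsening into a second, recurrent event. Section 9.1.3 does not support this. It reserves recurrence for an event that has resolved, so a recovering event remains persistent and keeps one record. A reader might further suppose that neuropathy improves slowly and that recovering will therefore be a common outcome. The documents do not say so; section 9.1.9.3 describes frequency, relatedness and an unclear onset and dose pattern.

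**Conclusion.** The end-date rule conflicts with the protocol's own outcome codes and with its definition of a persistent AE. If it is followed, the listed duration of every recovering event is cut short. That conclusion assumes only that duration is computed from the end date.

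The effect on AESI resolution is conditional. The overstatement of the percentage resolved is zero if resolution is defined by the recovered codes. It equals the recovering share if the end date drives the derivation or if recovering counts as resolved. The 5, 10 and 20 point figures, and the 40% against 60% example, rest on assumed shares and say nothing about the actual data.

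It is tempting to conclude that time to resolution will come out too favourable. The documents do not support that as a general statement: the SAP wording may exclude these events, and if it does not, the direction of the median is undetermined.

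The reach is narrow, since the incidence and highest-grade tables stand. The point still merits correction because a stated rule produces wrong durations and the resolution derivation is left open.

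**What to change.** 1. **Protocol sections 9.1.8 and 17.1.8:** delete recovering/resolving from the outcomes that require an end date, and leave the end date blank for those events.
2. **Analysis of existing records:** where the outcome is recovering/resolving and an end date is present, treat the event as not ended and show its duration as ongoing at last contact.
3. **SAP section 17.2 and Addendum section 3.5:** define resolution by outcome code as recovered/resolved, state whether recovered with sequelae counts, and state that recovering/resolving is unresolved.

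The cost is one outcome removed from a sentence that appears twice in the protocol, and one derivation rule. Items 2 and 3 can be applied to data already collected. The downside is that resolution percentages may become slightly less favourable than under a derivation driven by the end date.

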## **9.1.9 Adverse Events of Special Interest**

### **9.1.9.1 Constipation**

Constipation ( $\leq$  Grade 3) has been the most frequently reported clinically significant adverse event. The event seems to be treatment-related and dose-dependent.

Measures for handling AEs of constipation have been implemented in order to prevent severe toxicity of patients with constipation enrolled with mild gastrointestinal disorders and to minimize the risk of constipation evolving in patients enrolled without similar symptoms (please refer to Section 7.4.1 for prophylactic concomitant medications).

### **9.1.9.2 Neutropenia**

Neutropenia has been reported in  $> 20\%$  of patients at any dose/cohort. The majority of events was treatment-related, was reported in patients receiving dose of 2.0 mg/kg or more, and was from the 1Q3W arm, and recovered without dose change.

Measures for handling AEs of neutropenia include dose delays and dose reductions, please refer to Section 7.3.2.

### **9.1.9.3 Peripheral Neuropathy**

Peripheral neuropathy has been reported in  $> 20\%$  of patients at any dose/cohort. Although considered as treatment-related, onset latency and a deducible pattern based on dose-strength of enapotamab vedotin are unclear. The peripheral neuropathy will be assessed at the baseline and throughout the trial, when clinically indicated, to better understand its clinical course (Section 8.4.5).

Measures for handling AEs of peripheral neuropathy include dose delays and dose reductions, please refer to Section 7.3.2. Specific safety reporting requirements are in place for peripheral neuropathy (see Section 9.3.2)

Document Name: GCT1021-01 Protocol

Document Number: TMF-03326

Version: 11.0

---

#### **9.1.9.4 Immune-related Adverse Events**

Measures for handling immune-related AEs please refer to Section [7.3.3](#).

#### **9.1.10 Information about Infusion Related Reactions**

Information on whether AEs are infusion related or not must be reported in the eCRF.

#### **9.1.11 Serious Adverse Event**

Indicate whether or not the AE is determined to be “serious” based on what is defined in Section [9.2](#).

### **9.2 Definition of Serious Adverse Events**

The classification of the seriousness of the event determines the reporting procedures to be followed.

An AE that meets one or more of the following criteria/outcomes is classified as serious:

- Requires inpatient hospitalization or prolongation of existing hospitalization
- Results in persistent or significant incapacity or substantial disruption of the ability to conduct normal life functions
- Is a congenital anomaly/birth defect
- Medically important
- Results in death
- Is life-threatening

The term "life-threatening" in the definition of "serious" refers to an event in which the patient was at risk of death at the time of the event; it does not refer to an event which hypothetically might have caused death if it were more severe.

Elective surgery, overnight for convenience or other scheduled hospitalization periods that were planned before the patient was included in this trial are not to be considered serious. However, the event must be reported on the AE page in the eCRF and commented upon.

Medical and scientific judgment must be exercised in deciding whether an AE is believed to be “medically important”. Medical important events may not be immediately life-threatening or result in death or hospitalization but may jeopardize the patient or may require intervention to prevent one of the other outcomes listed in the definition above.

Document Name: GCT1021-01 Protocol

Document Number: TMF-03326

Version: 11.0

---

### **9.3 Events Requiring Immediate Reporting**

#### **9.3.1 Serious Adverse Events and Non-serious Grade 3 Adverse Events**

SAEs and non-serious Grade 3 AEs must be reported from the investigational site to the Safety CRO no later than 24 hours following a) the patient visit at which such AE was reported, noted or recognized; or b) the principal investigator's or any investigator personnel's receipt of the test results or other information at, or from which, such development was reported, noted or recognized. Grade 3 and 4 abnormal lab test results must be reported as AEs when these are assessed as clinically significant by the reporting investigator.

#### **9.3.2 Peripheral Neuropathy Adverse Events $\geq$ Grade 2 or Leading to Permanent Discontinuation of Enapotamab Vedotin Treatment**

All events of peripheral neuropathy  $\geq$  Grade 2 or leading to permanent discontinuation of enapotamab vedotin (regardless of grade) must be reported from the investigational site to the sponsor within 24 hours of knowledge of the event.

#### **9.3.3 Overdose and Medication Errors**

An overdose is defined as a patient receiving a dose of enapotamab vedotin in excess 10% of that specified in this protocol. All cases of overdose of enapotamab vedotin whether it resulted in an AE or not must be reported to the sponsor as protocol deviations and Safety CRO within 24 hours of knowledge of the event. It should also be recorded on the eCRF AE page.

Medication errors and uses outside what is foreseen in the protocol, including misuse and abuse of enapotamab vedotin must be reported to the sponsor as protocol deviations and Safety CRO within 24 hours of knowledge of the event. It should also be recorded on the eCRF AE page. Furthermore, AEs fulfilling the criteria in Section 9.2 must be reported accordingly.

Overdose, medication errors, misuse and abuse do not automatically make an AE serious, but if the consequences are serious, for example death or hospitalizations, the event is serious and must be reported as an SAE.

#### **9.3.4 Pregnancy**

Any pregnancy that occurs during trial participation must be reported. Pregnant trial patients must be withdrawn from treatment immediately, whereas male patients may continue in the trial should pregnancy of female partners occur. In this case, a separate informed consent will be obtained from the female partner for collection of information regarding the pregnancy.

Each pregnancy must be reported to the Safety CRO within 24 hours of learning of its occurrence. The pregnancy must be followed-up to determine outcome (including premature termination) and status of mother and child. The child must be followed at least to the age of one month.

Document Name: GCT1021-01 Protocol

Document Number: TMF-03326

Version: 11.0

Pregnancy complications and elective terminations for medical reasons must be reported as an AE or SAE. Spontaneous abortions must be reported as an SAE. Any SAE occurring in association with a pregnancy brought to the investigator's attention after the patient has completed the trial and considered by the investigator as possibly related to the enapotamab vedotin, must be promptly reported to sponsor or designee.

#### 9.4 Timelines for Reporting

The required timeframes and reporting forms for reporting SAEs, non-serious Grade 3 AEs, neuropathy Grade 2 AEs, neuropathy AEs leading to discontinuation, overdose, medication errors, and pregnancies are presented in [Table 24](#).

All new information regarding SAEs (initial and follow-up) must be reported from sites to sponsor within 24 hours. The final SAE report must be signed by a physician. Sites must respond to follow-up queries from sponsor within 3 days.

**Table 24. Timeframes for Reporting SAEs, Grade 3 AEs, Peripheral Neuropathy, Overdose and Medication Errors and Pregnancies**

Type of Event	Initial Reports		Follow-up Information on a Previous Report	
	Time Frame	Documents	Time Frame	Documents
All SAEs, Grade 3 AEs, neuropathy Grade 2 AEs, neuropathy AEs leading to discontinuation	24 hours*	Safety Reporting Form	3 days * 24 hours*	CDS SAE DCF Site SAE DCF
Overdose and Medication Errors	24 hours*	Safety Reporting Form	3 days * 24 hours*	CDS SAE DCF Site SAE DCF
Pregnancy	24 hours*	Pregnancy Form	3 days	Updated Pregnancy Form

*AE=adverse event; DCF=Data Clarification Form; CDS=Corporate Drug Safety; SAE=serious adverse event*

*\*no later than 24 hours/3 days following a) the patient visit at which such AE was reported, noted or recognized; or b) the principal investigator's or any investigator personnel's receipt of the test results or other information at, or from which, such development was reported, noted or recognized.*

Document Name: GCT1021-01 Protocol

Document Number: TMF-03326

Version: 11.0

---

communication set-up will include the following components:

- SAEs and non-serious Grade 3 AEs must be reported from the investigational site to the sponsor via the Safety CRO within 24 hours and medically evaluated following receipt. During the dose escalation part of the trial, at least biweekly safety/medical meetings to discuss AEs and laboratory data will be held with the participation of at least Drug Safety, sponsor medical officer and CRO Medical Monitor; and the safety data will be evaluated for individual treatment arms as well as across treatment arms. If safety signals warranting actions are identified in one treatment arm, actions will be implemented in the other treatment arm if deemed relevant for the specific signal in question.
- Monthly telephone conferences between all participating Investigators, CRO Medical Monitor and sponsor will be arranged. Pending severity of observed safety signals, ad hoc meetings will be held.
- A contact list with all participating investigators will be available at all sites.
- 24 hours/7 days a week availability of [REDACTED] Medical Monitor.
- Direct telephone link from investigator to sponsor medical officer.
- DMC meetings following each cohort and ad hoc as needed. Ad-hoc DMC meetings may be called for by both the DMC and Sponsor any time during the escalation and expansion phases of the trial if new safety data warrants immediate action to the conduct of the trial. The outcome of the DMC meeting will be discussed and confirmed by the sponsor safety committee and ultimately communicated to the investigators following each meeting.
- Investigators or their representative(s) may participate in the open part of the DMC meetings if deemed relevant.

Document Name: GCT1021-01 Protocol

Document Number: TMF-03326

Version: 11.0

---

